4.3 Changes to Analysis from Protocol

Concomitant medications will be collected in relation to adverse events and medical device incidents only. For this reason, the summary of concomitant medication will be provided on randomised analysis set only as no data will be collected for patients screened and not randomised.

Document:	Y:\Kimberly-Clark\DryNites\Documentation\SAP\DryNites_SAP_v1.0_20200203		
Author:	[name] Version Number:		1.0
		Version Date:	03Feb2020
Template No.: RWI_TP_BIOS0013 Revision 1			Reference: RWI_WI_BIOS0015
Effective Date: 15Jun2018			

Safety set definition will be modified to include all patients exposed to DryNites for at least 1 night after signature of informed consent.

Treatment emergent adverse events will be defined as all events occurred or worsened in severity after the start of the screening period.

5. PLANNED ANALYSES

5.1 Interim Analysis

Not applicable

5.2 Final Analysis

All final, planned analyses identified in this SAP will be performed by IQVIA Real-World Evidence Solutions (RWES) Biostatistics following Sponsor Authorisation of this Statistical Analysis Plan.

The analysis on primary and secondary endpoints will be performed once the last randomised patients will complete the intervention period. At the time of this analysis the database will not be locked if at least one participant is still ongoing on extension study period.

The full set of analyses will be updated, when applicable, after the official database lock, occurring after the completion of the Visit 4 by the last patient accepting to participate to the extension period.

6. ANALYSIS SETS

6.1 All Patients Screened Set

The all screened (SCR) set will contain all patients who provide informed consent for this study.

Document:	Y:\Kimberly-Clark\DryNites\Documentation\SAP\DryNites_SAP_v1.0_20200203		
Author:	[name] Version Number:		1.0
		Version Date:	03Feb2020
Template No.: RWI_TP_BIOS0013 Revision 1		Refere	ence: RWI_WI_BIOS0015
Effective Date: 15Jun2018			

6.2 Randomised Set

The randomised set (RND) will contain patients in the Screened Set who are assigned to a randomisation group.

6.3 Safety Analysis Set

The safety analysis set (SAF) will contain all patients exposed to DryNites® for at least 1 night after signature of informed consent.

6.4 Primary Analysis Set

The primary analysis set (PAS) will contain all patients in the Randomised Set excluding participants with major violations of the clinical investigation plan.

The following violation will be considered as major:

- Absorbent pants/nappies (of any brand) used nocturnally in the 'no pants' group (≥3 nights showing violation of the clinical investigational plan over the 4-week trial period will merit exclusion; these will be documented in the diary)
- No pants, or absorbent pants of a different brand, used nocturnally in the DryNites[®] group (≥3 night showing violation of the clinical investigation plan over the 4-week trial period will merit exclusion; these will be documented in the diary)
- Bed mat not used (≥3 nights showing violation of the clinical investigation plan over the 4week trial period will merit exclusion; these will be documented in the diary)
- Initiation of a prescribed therapy for NE (pharmacologic or bed alarm).

Document:	Y:\Kimberly-Clark\DryNites\Documentation\SAP\DryNites_SAP_v1.0_20200203		
Author:	[name] Version Number:		
		Version Date:	03Feb2020
Template No.: F	RWI_TP_BIOS0013 Revision 1		Reference: RWI_WI_BIOS0015

Effective Date: 15Jun2018

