# 4 METHODOLOGY

# 4.1. Study Design

This is an 8-week randomised, open-label, 2-arm, parallel-group Phase IV trial with a 2:1 allocation ratio for discontinuation of continuation of use of DryNites® absorbent pants in children with NE, with an optional 4-week extension period. This will be an equivalence trial for the primary endpoint.

Eligible patients are children with monosymptomatic NE, not previously treated for NE, and managed with absorbent pants/nappies (any brand) for a minimum of 6 months. Participants must be dry at day for at least 6 months. Participants will be divided in 2 age groups of similar

size. The younger age group will be comprised of participants aged 4-<6 years old and the older age group will be comprised of participants aged  $\ge 6-8$  years old. Capping of the faster recruiting subgroup will be implemented if needed.

Participation in the study will be proposed for all children meeting the above conditions; parents/carers should be given sufficient time to review the study information and provide informed consent to their child's and their participation. Children's assent will be requested for the older age group.

The study consists of 3 consecutive periods of 4 weeks each, including the run-in, the intervention (core trial) period, and the extension period.

Participant meeting the eligibility criteria will enter the run-in period. During the 4-week run-in period, all participants will be assigned to using DryNites® every night.

Participant meets the inclusion criterion of NE 7 nights per week during the last week of the run-in period will be randomised to participate in the intervention (core trial) period. During the 4-week intervention period, participants will be assigned to either stopping the use of absorbent pants or continuing DryNites® in a 2:1 ratio. All participants will receive absorbent bed mats to use every night, however, the use of bed mats is optional.

Following completion of the 4-week intervention period, participants will be invited to participate in the optional 4-week extension. During the optional 4-week extension period, participants will remain on their randomly assigned treatment for an additional 4 weeks.

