# 4.3.8. Clinical Investigation Plan Deviations

The following events will be considered as the major violations of the clinical investigation plan and lead to the exclusion of the participant's data from the analysis:

- Absorbent pants/nappies (of any brand) used nocturnally in the 'no pants' group (up
  to 4 violations of the clinical investigational plan over the 4-week trial period will
  merit exclusion; these will be documented in the diary)
- No pants, or absorbent pants of a different brand, used nocturnally in the DryNites® group (up to 4 violations of the clinical investigation plan over the 4-week trial period will merit exclusion; these will be documented in the diary)
- Initiation of a prescribed therapy for NE (pharmacologic or bed alarm)

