# **4.4.2.** Provision of Study Treatment

DryNites®, defined as the study treatment, is commercially available medical device of Class I and will be provided free of charge to the study participants. DryNites® should be used in accordance to this clinical investigation plan instructions. Study treatment and absorbent bed mats will be supplied to the participants by the Investigator/site; however, the use of bed mats is optional. A 4-week supply will be distributed to each participant's parents/carers at each visit Day 0, Day  $28 \pm 7$  days, and Day  $56 \pm 7$  days. In case of remote visits, study materials will be shipped by the site to the patient's address according to local law and regulatory instructions. All packages will be labelled "for use in clinical investigation only" (in the applicable local languages).

The younger age group will be provided with the 4–7 years DryNites® size. Parents/carers in the older age group will select whether age 4–7 or age 8–15 DryNites® size is most appropriate. DryNites® age 4–7 years are provided in packs of 10. As such, each participant will be provided with 4 packs of DryNites® to cover each 4-week period.

DryNites® age 8–15 years are provided in packs of 13. As such, each participant will be provided with 3 packs of DryNites® to cover each 4-week period.

Absorbent bed mats are provided in packs of 12. Each participant randomised in the intervention group (discontinuation of DryNites® pants) will be provided with 3 packs of bed mats to cover each 4-week period. Participants randomised in the control group (continuation of DryNites® pants) will receive 1 pack of bed mats per 4-week period. The use of bed mats is optional.

Any surplus of DryNites® and absorbent bed mats at the end of each 4-week period can be kept by the participant.

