#### 4.7.2. Direct-to-Patient Data Collection

The following data will be collected daily for all enrolled patients using an electronic diary from the morning following the baseline visit until discontinuation from the study:

- Were absorbent pants worn? Yes/No/Another brand
- Was the bed mat used? Yes/No/Another brand
- Did the child have an NE event? Yes/No
- How was the NE event managed? One response to be selected: Child slept through the night; child awoke but did not take any action; child awoke and changed pants/changed bed/visited toilet but did not disturb parents; child awoke and woke parents.

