2. INTRODUCTION

This statistical analysis plan (SAP) describes the rules and conventions to be used in the presentation and analysis of equivalence in spontaneous resolution of nocturnal enuresis (NE) in children, between discontinuation of nocturnal use of absorbent pants, compared with continued use of absorbent pants, over a period of 4 weeks. It describes the data to be summarised and analysed, including specifics of the statistical analyses to be performed.

This SAP is based on clinical investigation plan version 1.0, dated 11 February 2019 and case report forms (CRFs) version 1.0, dated 29 October 2019

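### SAP 6.4 excludes children from the Primary Analysis Set for not using a bed mat, which the protocol makes optional, and the two documents' pants-use exclusion rules conflict

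*SAP*

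**What the plan says.** **Bed mats.** SAP 6.4 lists four major violations that remove a randomised child from the Primary Analysis Set. One is "Bed mat not used (≥3 nights showing violation of the clinical investigation plan", counted from the diary over the 4-week trial period. Protocol 4.1 says "All participants will receive absorbent bed mats to use every night, however, the use of bed mats is optional"; the synopsis, section 2 and section 4.4.2 also call mat use optional. The major violations in protocol 4.3.8 do not include mats.

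**Supply.** Under protocol 4.4.2, each child in the discontinuation (no-pants) arm "will be provided with 3 packs of bed mats to cover each 4-week period", whereas "Participants randomised in the control group (continuation of DryNites® pants) will receive 1 pack of bed mats per 4-week period". A pack holds 12 mats. The same section adds: "Any surplus of DryNites® and absorbent bed mats at the end of each 4-week period can be kept by the participant".

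**Pants use.** SAP 6.4 excludes at 3 or more nights of use contrary to the assigned arm. Protocol 4.3.8 says "up to 4 violations of the clinical investigation plan over the 4-week trial period will merit exclusion".

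**Versions.** SAP section 2 states: "This SAP is based on clinical investigation plan version 1.0, dated 11 February 2019". The current protocol is version 3.0 of 28 January 2022.

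**Use of the set.** Protocol 5.4.2 and SAP 15.1.3 place the equivalence confidence interval on the Primary Analysis Set. On the Randomised Set, diary data are only described (protocol 5.4.2, SAP 15).

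**The concern.** Two current documents define the population for the primary conclusion differently. Under the SAP, a child who followed protocol version 3.0 exactly but slept without a mat on 3 nights is excluded; under the protocol that child is kept. A child with 3 or 4 nights of wrong pants use may be in or out, depending on the document and on how 4.3.8 is read.

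These exclusions are made after randomisation, in an open-label trial, on behaviour that is likely to differ by arm. They could therefore disturb the comparability of the arms as well as reduce numbers. The planned outputs would not settle the question. Counts by analysis set (SAP 10), and baseline tables repeated if more than 15% are excluded (SAP 7), show that children were lost. They do not show whether equivalence depends on losing them. The only planned sensitivity analysis of the primary variable is multiple imputation when 20% or more is missing (SAP 15.1.2 and 15.1.4), which does not concern excluded children.

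**Working it through.** **1. The plan's own figures (protocol 5.2).** Per age group, 15 continuation children are needed, so 3 × 15 = 45 at 2:1. Adding 15 gives 60. At 2:1, 60 × 1/3 = 20 continuation children at most. The buffer is 20 − 15 = 5, or 5/20 = 25%, and it must also cover dropouts, poor compliance and screen failures.

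The stated power is 99%. Simulating as described (7 nights per child, wet-night probabilities 0.95 and 0.80, 15 against 30 children, 95% interval within ±2/7 on the proportion scale, independent nights) gives 97.8% with a Wald interval on pooled nights, 97.2% with a Welch interval and about 91% with the pooled t interval. The stated figure is roughly reproduced by the first two methods.

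**2. What the mat rule demands.** Exclusion starts at 3 no-mat nights, so at most 2 are allowed: 28 − 2 = 26 mat nights are needed.

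**3. Nights each mat must cover.** The formula is 26 / (period supply + mats carried over from run-in). The run-in quantity per child is not stated, so the carry-over is an assumption, taken as equal in both arms.

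| Carry-over | Continuation (12 mats) | No pants (36 mats) |
|---|---|---|
| 0 | 26/12 = 2.17 | 26/36 = 0.72 |
| 6 | 26/18 = 1.44 | 26/42 = 0.62 |
| 12 | 26/24 = 1.08 | 26/48 = 0.54 |
| 14 | 26/26 = 1.00 | 26/50 = 0.52 |
| 24 | 26/36 = 0.72 | 26/60 = 0.43 |

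With no carry-over, 12 mats used for 1, 2 or 3 nights each leave 28 − 12 = 16, 28 − 24 = 4 or 0 no-mat nights in the continuation arm. The first two exceed the limit. In the no-pants arm, 36 mats leave none. Visits may fall 7 days early or late: at one mat per night, 12 mats leave 9 no-mat nights in 21 and 23 in 35.

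**4. Mats in ample supply.** The rule is strict even then. If each night is independently mat-free with probability 5%, 10% or 20% (assumed), the chance of 3 or more such nights in 28 is 16%, 54% or 94%.

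**5. Pants-use rules side by side.** Protocol 4.3.8 can be read literally or as a tolerance of 4.

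| Nights contrary to arm | SAP 6.4 | 4.3.8, literal | 4.3.8, tolerance of 4 |
|---|---|---|---|
| 1–2 | kept | excluded | kept |
| 3–4 | excluded | excluded | kept |
| 5 or more | excluded | not addressed | excluded |

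At an assumed independent 5% deviation rate per night over 28 nights, the share excluded is 16% under the SAP, 75% under the literal reading and 1.2% under the tolerance reading. A third reading, exclusion from the fourth night, gives 4.9%.

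**6. Effect of losing continuation children.** With 30 no-pants children in an age group and the assumptions of step 1:

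| Continuation children | Pooled t power | Wald power |
|---|---|---|
| 15 | 91% | 98% |
| 10 | 79% | 97% |
| 5 | 44% | 93% |
| 2 | 12% | 80% |

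With the age groups pooled, 20 against 80 still gives above 99% (pooled t) and 10 against 80 gives 89%.

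**The case against.** - **The mat item may be void.** It counts nights that violate the clinical investigation plan, and under version 3.0 a night without a mat violates nothing. This reading is fair, but it is an inference. The item is still listed as major and points to a diary field, so one programmer could apply it and another ignore it.
- **The supply argument joins a rule written to version 1.0 with quantities from version 3.0, and carry-over could remove the shortage.** Part of this stands. A carry-over of 14 or more mats means that no continuation child needs to reuse one, nothing says mats are single-use, and the diary ("Was the bed mat used? Yes/No/Another brand") allows other brands. With equal carry-over the continuation arm still has fewer mats per night. The unequal supply also suggests that the plan expects less mat use there.
- **The buffer of 5 applies only within an age group.** This is correct. SAP 15.1.3 tests the whole set and then repeats by age, where up to 40 continuation children give more room. However, protocol 5.2 sizes each age group separately, and SAP 15.1 describes the primary analysis as separate by age group.
- **The literal pants-use reading is implausible.** The amendment table says the rule was relaxed, which favours a looser rule than 3 or more nights. Even so, the current sentence does not say this, and the conflict at 3 nights or more remains.
- **Descriptive Randomised Set summaries may suffice.** They may allow a rough comparison of means, but they are not a planned interval to set against the margin.

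**Conclusion.** The concern holds and should be corrected before analysis. That SAP 6.4 and protocol version 3.0 disagree on mats and on pants use is a matter of current text and needs no assumption. It bears directly on the primary conclusion, because no equivalence interval is planned on any other set.

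The difference by arm is likely but not quantified. From the period's supply alone it is 2.17 against 0.72 nights per mat. It narrows with carry-over, and no continuation child is forced to reuse a mat once carry-over reaches 14. The share of children lost to the mat rule cannot be predicted from the documents. Within an age group, losing more than 5 of 20 continuation children for all reasons together takes the arm below its planned 15; the pooled analysis tolerates more. The power figures rest on independent nights and a margin on the proportion scale.

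**What to change.** 1. In SAP 6.4, delete the bed-mat item. In SAP section 2, rebase the SAP on protocol version 3.0 of 28 January 2022.
2. Reconcile the pants-use exclusion in SAP 6.4 and protocol 4.3.8 into one rule, stated as a number of nights and confirmed by the sponsor before analysis. This review does not propose the threshold.
3. In SAP 15.1.3, add: *As a supportive sensitivity analysis, the same 95% CI for the difference in means will be presented for the Randomised Set, overall and by age group.* The success criterion stays on the Primary Analysis Set.

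The cost is a SAP update, a one-line protocol clarification and one extra table. The Randomised Set interval includes children who did not follow their assigned arm. That can pull the arms together and favour equivalence, so it should be read as supportive only.

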6.5 Extension Analysis Set

The extension analysis set (EAS) will contain all patients in the Randomised Set who participate in the extension period.

7. GENERAL CONSIDERATIONS

Continuous variables will be reported as mean (and standard deviation [SD]) along with median and range where appropriate.

The minimum and maximum will be reported to the same number of decimal places as the raw data recorded in the database. The mean and median will be reported to 1 decimal place while the SD will be reported to 2 decimal places.

Categorical variables will be summarised as number and proportion of the total study population, and by age subgroups (4–<6 years and \geq 6–8 years) where appropriate.

In general, descriptive statistics of quantitative parameters (result and change from baseline) by scheduled visits will be provided on observed cases, that is, patients having non-missing assessments at a specific visit. Percentages will then not include the missing category, but the count of missing observations will be provided. Percentages will be presented to 1 decimal place except percentages equal to 100 that will be presented as 100% and zero frequencies that will be presented as 0%.

Confidence intervals (CI) and statistical tests will be 2-sided unless otherwise specified. P-values, which are greater than or equal to 0.0001, and less than or equal to 0.9999, will be presented to 4 decimal places. All other p-values, which are less than 0.0001, will be presented as <0.0001. Individual patient data will be presented in listings considering the Screened Set.

Document:	Y:\Kimberly-Clark\DryNites\Documentation\SAP\DryNites_SAP_v1.0_20200203		
Author:	[name] Version Number:		
		Version Date:	03Feb2020
Template No.:	RWI_TP_BIOS0013 Revision 1		Reference: RWI_WI_BIOS0015

Effective Date: 15Jun2018

Descriptive analyses will be performed on the SCR Set and the RND Set to gain an understanding of the qualitative and quantitative nature of the data collected and the characteristics of the sample studied. If more than 15% of randomised participants will be excluded from the PAS, the baseline descriptive analysis will be repeated on the primary endpoint analysis population.

7.1 Reference Start Date

Reference start date is defined as the day of the randomisation and will appear in every listing where an assessment date or event date appears.

7.2 Baseline

Baseline is defined as the last non-missing measurement taken prior to reference start date (including unscheduled assessments). In the case where the last non-missing measurement and the reference start date coincide, that measurement will be considered pre-baseline, but AEs and medications commencing on the reference start date will be considered post-baseline.

7.3 Windowing Conventions

The following table describes assignment of visit windows to the following data for purposes of analysis:

Table A:Windowing

Assigned Study Day (Inclusive)		Visit Assigned	
From	То		
-35	0	Visit 1	
1	1	Visit 2	
2	42	Visit 3	

Template No.: RWI_TP_BIOS0013 Revision 1

Reference: RWI_WI_BIOS0015

Effective Date: 15Jun2018

43 63 Visit 4

To define cut on visits to the patient's diary, visit date will be used as reference along with windowing conventions.

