**Table 1 Study Objectives and Endpoints** 

Objectives	Endpoints
Primary	
To determine if discontinuing the use of DryNites® absorbent pants over a period of 4 weeks has any impact on the rate of spontaneous resolution of NE compared with continuing use of DryNites® absorbent pants	Average number of wet nights in Week 8 (last week of the intervention period)
Secondary	
To determine if using DryNites® absorbent pants improves the child's Quality of Life (QoL) assessed by the Paediatric Incontinence Questionnaire (PinQ) compared with not using absorbent pants	• Change from baseline in total PinQ score at Day 56 ± 7days
To determine if using DryNites® absorbent pants improves the parent/carer's QoL assessed by the World Health Organization Quality of Life BREF (WHOQoL-BREF) compared with not using absorbent pants	• Change from baseline in total score of each domain at Day $56 \pm 7$ days
To determine if using DryNites® absorbent pants improves the child's sleep assessed by the Paediatric Daytime Sleepiness Scale (PDSS) compared with not using absorbent pants	• Change from baseline in total PDSS score at Day 56 ±7 days
To determine if using DryNites® absorbent pants improves the parent/carer's sleep assessed by the Checklist Individual Strength questionnaire (CIS) compared with not using absorbent pants	Change from baseline in subscale scores at Day 56     ±7 days
To determine if DryNites® absorbent pants offer different benefits or limitations to previously used absorbent pants/nappies	Descriptive statistics

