## 4.7.6. Disposition/End of Study

The following data will be collected for all enrolled patients at the time of discontinuation:

- AEs occurred since the previous visit. All AEs ongoing at the time of discontinuation will be followed up until resolution or stabilisation of for 30 days, whichever occurs first
- Concomitant medication for AEs
- Review of diary data
- PROs: PinQ, WHOQOL, PDSS, CIS (for participants who were randomised)
- Date of completion/discontinuation
- Primary reason for discontinuation

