15.1.1 Primary Analysis Variable & Derivation

The primary analysis variable will be the difference between the 2 groups on the average number of wet nights in Week 4 of the intervention study period and will be derived using the item "Did the child have an NE (nocturnal enuresis) event?" collected on daily diary. The number of "Yes" for each patient will be counted over the last 7 days of the intervention period (from randomisation till the Visit 3 day).

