15.2.3 Analysis of Secondary Variables

15.2.3.1 Analysis of Secondary Variables

Analyses of PinQ, WHOQoL-BREF, PDSS and CIS questionnaires will be provided by group on the Randomised Set.

Frequency distribution and descriptive statistics, when applicable, will be provided by visit for each item of questionnaires, while summary statistics for total scores, domain scores and changes from baseline will be provided as applicable.

The effect size will be also presented as descriptive statistics of ratio between the change from baseline and baseline SD.

Document:	Y:\Kimberly-Clark\DryNites\Documentation\SAP\DryNites_SAP_v1.0_20200203		
Author:	[name]	Version Number:	1.0
		Version Date:	03Feb2020
Template No.: F	RWI_TP_BIOS0013 Revision 1		Reference: RWI_WI_BIOS0015
Effective Date:	15Jun2018		

The percentage of patients with change from baseline ≥ 0.5 time the baseline SD will be also provided.

For applicable questionnaires an ANCOVA with baseline PROs value as covariate will be performed. Group comparisons will be performed for the difference in least squares means (LSMean) at Visit 3. The LSMean (standard error [SE]) by group and visit (if applicable), the LSMean difference between groups, along with 95% confidence limits of the group differences and the p-value for the group comparison will be displayed as purely exploratory. For the change from baseline, p-value for the within-group difference will also be displayed as purely exploratory. The Absorbent Pants Clinical Trial Questionnaire administered at study entry, and the DryNites® Clinical Trial Questionnaire administered at the end of the run-in period, will be analysed descriptively for the Screened Set.

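### SAP Table A labels study days 2 to 42 as Visit 3, so early-discontinuation and late Visit 2 questionnaires can be analysed as Day 56 data, and the SAP gives no rule for the Week 4 diary of a child who stops early

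*SAP*

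**What the plan says.** **Day count and windows.** SAP 7.1 fixes the origin: "Reference start date is defined as the day of the randomisation". Table A in SAP 7.3 puts Visit 2, the randomisation visit, on study day 1 alone, so randomisation is day 1. It gives days 2 to 42 to Visit 3 and days 43 to 63 to Visit 4. On the diary it adds: "To define cut on visits to the patient's diary, visit date will be used as reference along with windowing conventions".

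**Questionnaires.** Protocol 4.1 places randomisation at Day 28 ± 7 and Visit 3 at Day 56 ± 7, both counted from baseline. Protocol Table 1 defines the PinQ endpoint as "Change from baseline in total PinQ score at Day 56" with the same ± 7 days, and times the WHOQoL-BREF, PDSS and CIS endpoints alike. SAP 15.2.3.1 states: "Group comparisons will be performed for the difference in least squares means (LSMean) at Visit 3". It uses the Randomised Set and calls the p-values purely exploratory. Protocol 4.7.6 begins: "The following data will be collected for all enrolled patients at the time of discontinuation". Its list includes all four questionnaires for randomised children. Protocol 4.3.6 keeps withdrawn children's data for analysis. Protocol 4.1 and 4.5.2 allow forms to be completed remotely after a visit, up to the next one.

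**Primary diary variable.** SAP 15.1.1 names "the average number of wet nights in Week 4 of the intervention study period" as the target and counts Yes answers "counted over the last 7 days of the intervention period (from randomisation till the Visit 3 day". SAP 15.1.2 brings in multiple imputation when 20% or more of primary values are missing. The SAP has no early-termination category, no rule for several assessments in one window, and no minimum number of diary nights.

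**The concern.** The lower limit of the Visit 3 window is the day after randomisation, yet Visit 3 stands for the end of a four-week intervention. Anything dated in the first days after randomisation takes the end-of-intervention label unless another rule removes it, and none does.

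For the questionnaires, this puts forms that reflect a few days of the assigned regimen into a comparison defined at Day 56 ± 7.

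For the primary variable, the value of an early stopper is left to whoever programs it. All children are randomised at 7 of 7 wet nights, so a week taken soon after randomisation is likely to be near 7/7 in both arms. Protocol 5.4.6 itself warns of finding equivalence because neither group changed. A child given a value in this way is also not missing, so SAP 8.3 and the 20% trigger would not reach that child.

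**Working it through.** **1. Plan's own figure, to confirm the inputs.** Protocol 5.2 gives 99% power with 15 continuation children (30 in the other arm), wet-night probabilities 0.95 and 0.80, margin 2/7 and a 95% CI. With 7 nights per child (105 and 210 nights):

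SE = √(0.95×0.05/105 + 0.80×0.20/210) = 0.0348

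Power = Φ((2/7 − 0.15)/0.0348 − 1.96) = 0.9735

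Simulating the same interval gives 97.7%. Both are within 2 points of 99%.

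**2. Where a compliant visit can fall** (randomisation Day 21–35, Visit 3 Day 49–63, Visit 4 Day 77–91; study day 1 = randomisation).
- Visit 3 earliest: 49 − 35 + 1 = study day 15. Latest: 63 − 21 + 1 = study day 43.
- Four weeks ± 7 days from the child's own randomisation: 29 ± 7 = study days 22 to 36.
- Visit 4 latest: 91 − 21 + 1 = study day 71.

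Table A's Visit 3 window has 41 days. Days 2–14 (13 of 41) can never be a compliant Visit 3, and days 2–21 (20 of 41) come before four weeks minus 7 days. At the other end, a compliant Visit 3 on day 43 is labelled Visit 4, and a compliant Visit 4 after day 63 has no label.

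**3. Questionnaires, rule by rule.** A child who discontinues on study day 5 completes the four forms under Protocol 4.7.6. Day 5 lies in 2–42, so the label is Visit 3 and the forms reach the Visit 3 ANCOVA. A Visit 2 form completed remotely on study day 3 takes the same label. SAP 7.2 would not accept it as baseline because it is dated after the reference start date, so that child may also lack the covariate.

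**4. Primary diary.** If a discontinuation on day 12 were treated as the Visit 3 day, the counted week would be days 6–12. A child stopping on study day s has at most s − 1 nights since randomisation: 1 night at s = 2, 6 at s = 7, and a full 7 only from s = 8. Stoppers on days 2–7 would therefore look drier simply for lack of nights, while later early stoppers are pulled towards 7/7 wet.

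**5. Size under the 7/7-wet reading.** Assumptions, none of them in the documents: a share f of children stop early and are counted as 7/7 wet, and all others follow their arm's Week 4 rate. The margin is read as 2 of 7 nights. With f in both arms, the expected difference is (1 − f) × the true one: 0.15 becomes 0.135 at f = 10%, and 2/7 becomes 0.257.

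False equivalence was simulated with the pooled t interval on each child's proportion of wet nights, true rates 0.95 and 0.95 − 2/7, and 20,000 trials per cell (Monte Carlo SE at most √(0.25/20,000) = 0.35 points):

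| f | 15 vs 30, both arms | 40 vs 80, both arms | 15 vs 30, no-pants arm only | 40 vs 80, no-pants arm only |
|---|---|---|---|---|
| 0 | 0.90% | 0.82% | 0.93% | 0.96% |
| 5% | 1.86% | 3.26% | 2.31% | 4.19% |
| 10% | 3.55% | 8.48% | 4.88% | 11.91% |
| 20% | 11.73% | 35.07% | 16.54% | 48.52% |
| 25% | 18.22% | 53.52% | 25.69% | 70.03% |

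15 vs 30 is the planning size per age group; 40 vs 80 is the full 120 at 2:1. The f = 25% row is an outer bound: the plan's allowance of 15 in 60 also covers poor compliance and screen failures.

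**The case against.** The strongest objection concerns the primary endpoint. A reader might infer that the SAP orders an early stopper's diary to be cut at the discontinuation date and counted as Week 4. The documents do not say so. SAP 15.1.1 names Week 4, and SAP 15.1.2 refers to the last week of the four-week period after randomisation. Protocol 4.7.4 (Visit 3) and 4.7.6 (disposition) are separate events with separate columns in Protocol Table 2. Treating the child as missing fits this text at least as well, and a child lost without any visit has no visit date to cut on. This stands: the harmful reading is permitted, not prescribed.

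A reader might also infer that the bias always favours equivalence. It does not: step 4 shows the opposite for stoppers on days 2–7. In addition, SAP 6.4 removes some children who abandon their assigned regimen. Nor can one divide the margin by the share of children who remain and call the result the true difference that would pass, because success needs the whole 95% CI inside the margin.

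Two further points stand in part. The questionnaire ANCOVA is exploratory, and SAP 8.1 plans no confirmatory testing. Using discontinuation forms is also a defensible way to avoid a completers-only comparison, but then the SAP should choose it openly, and that argument does not cover late Visit 2 forms. Finally, Table A says it applies to listed data, and no list is visible in the text available, so the claim is limited to the questionnaires and the diary.

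**Conclusion.** The concern holds in a limited form. For the questionnaires it follows from the written rules: Table A admits 13 days on which no compliant Visit 3 can occur, and it mislabels a compliant Visit 3 on day 43. The affected analysis is exploratory.

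For the primary endpoint the fault is a gap. The SAP does not say what value an early stopper receives, and one open reading would give that child a Week 4 value and keep the child out of the missing-data count. Under that reading, with 10% early stoppers in both arms counted as 7/7 wet and the true difference at a 2-night margin, false equivalence rises from about 1% to about 4% (15 vs 30) or 8% (40 vs 80). These figures rest on an assumed early-stop share and on all stoppers being fully wet. They show what the gap could cost; they do not predict what will happen in this trial.

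**What to change.** In SAP 7.3:
- Anchor the Visit 3 window to four weeks after the child's own randomisation, for example study days 22 to 43, and adjust the Visit 4 limits to match (a compliant Visit 4 can fall as late as day 71).
- Map forms by the nominal visit they belong to, so that a late Visit 2 form is not Visit 3.
- Label discontinuation assessments before the window as early termination. Summarise them separately and keep them out of the main Visit 3 ANCOVA, with a sensitivity analysis that includes them.

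In SAP 15.1.1 and 15.1.2:
- State that a discontinuation date is not the Visit 3 day.
- Set the primary value to missing when the diary ends before the fourth post-randomisation week or has fewer than a stated minimum of nights, and count these children towards the 20% trigger.
- Give an explicit rule for compliant but early Visit 3 dates (study days 15 to 21), for example using diary nights recorded after the visit up to study day 28 where available. Such nights may exist only for children who continue into the extension, so the rule must also cover those who do not.

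The cost is SAP wording, programming and one added sensitivity analysis. Slightly more data will be reported as missing and the Visit 3 N will be slightly smaller. Sites do nothing different.
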